## **4 STUDY DRUG**

Study drug includes both Investigational [Medicinal] Product (IP/IMP) and Non-investigational [Medicinal] Product (Non-IP/Non-IMP) see [Table 4-1](#) and can consist of the following:

- All products, active or placebo, being tested or used as a comparator in a clinical trial.
- Study required premedication, and
- Other drugs administered as part of the study that are critical to claims of efficacy (eg, background therapy, rescue medications)
- Diagnostic agents: (such as glucose for glucose challenge) given as part of the protocol requirements must also be included in the dosing data collection.

#### **4.1 Investigational Product**

An investigational product, also known as investigational medicinal product in some regions, is defined a pharmaceutical form of an active substance or placebo being tested or used as a reference in a clinical study, including products already with a marketing authorization but used or assembled (formulated or packaged) differently than the authorized form, or used for an unauthorized indication, or when used to gain further information about the authorized form.

The investigational product should be stored in a secure area according to local regulations. It is the responsibility of the investigator to ensure that investigational product is only dispensed to study subjects. The investigational product must be dispensed only from official study sites by authorized personnel according to local regulations.

For this study the investigational product is BMS-936558 (nivolumab).

#### **4.2 Non-investigational Product**

Other medications used as support or escape medication for preventative, diagnostic, or therapeutic reasons, as components of the standard of care for a given diagnosis, may be considered as non-investigational products.

#### **4.3 Storage and Dispensing**

The product storage manager should ensure that the study drug is stored in accordance with the environmental conditions (temperature, light, and humidity) as determined by BMS. If concerns regarding the quality or appearance of the study drug arise, the study drug should not be dispensed and contact BMS immediately.

Study drug not supplied by BMS will be stored in accordance with the package insert.

Investigational product documentation (whether supplied by BMS or not) must be maintained that includes all processes required to ensure drug is accurately administered. This includes documentation of drug storage, administration and, as applicable, storage temperatures, reconstitution, and use of required processes (eg, required diluents, administration sets).

The product storage manager should ensure that the study drug is stored in accordance with the environmental conditions (temperature, light, and humidity) as determined by BMS. If concerns regarding the quality or appearance of the study drug arise, the study drug should not be dispensed and contact BMS immediately.

Investigational product documentation (whether supplied by BMS or not) must be maintained that includes all processes required to ensure drug is accurately administered. This includes documentation of drug storage, administration and, as applicable, storage temperatures, reconstitution, and use of required processes (eg, required diluents, administration sets).

Infusion-related supplies (eg IV bags, in-line filters, 0.9% NaCl solution) will not be supplied by the sponsor and should be purchased locally if permitted by local regulations.

For non-investigational product, if marketed product is utilized, it should be stored in accordance with the package insert, summary of product characteristics (SmPC), or similar.

Please refer to the current version of the Investigator Brochure and/or pharmacy reference sheets for complete storage, handling, dispensing, and infusion information for BMS-936558 (nivolumab).

Nivolumab (BMS-936558) vials must be stored at a temperature of 2°C to 8°C and should be protected from light, freezing, and shaking. If stored in a glass front refrigerator, vials should be stored in the carton. Recommended safety measures for preparation and handling of nivolumab include laboratory coats and gloves.

For details on prepared drug storage and use time of nivolumab under room temperature/light and refrigeration, please refer to the BMS-936558 (nivolumab) Investigator Brochure section for “Recommended Storage and Use Conditions” and/or pharmacy reference sheets. Care must be taken to assure sterility of the prepared solution as the product does not contain any antimicrobial preservative or bacteriostatic agent. No incompatibilities between nivolumab and polyolefin bags have been observed.

Please refer to the current BMS-936558 (nivolumab) Investigator Brochure: Preparation instructions for details on the administration of nivolumab.

#### **4.4 Method of Assigning Subject Identification**

After the subject’s eligibility is established and informed consent has been obtained, the subject will be enrolled and a number will be assigned through an interactive voice response system (IVRS). Also, the IVRS will be used to manage enrollment of subject subgroups. Specific instructions and procedures for using IVRS will be provided to the investigational site in a separate document/ manual.

The investigator (or designee) will register the subject for enrollment by following the enrollment procedures established by BMS. The following information is required for enrollment:

- Date of informed consent
- Date of birth
- Gender at birth
- Confirmed RCC histology
- Confirmed presence or absence of brain metastases

#### **4.5 Selection and Timing of Dose for Each Subject**

Subjects will receive treatment every 2 weeks with 240 mg of nivolumab as a 30 minute ( $\pm$  5 minutes) IV infusion.

There will be no dose escalations or reductions of nivolumab allowed. Subjects may be dosed no less than 12 days from the previous dose. There are no premedications recommended for nivolumab on the first cycle. If an acute infusion reaction is noted, subjects should be managed according to [Section 4.5.5](#).

#### **4.5.1 Management Algorithm for Nivolumab related adverse events**

Immuno-oncology (I-O) agents are associated with AEs that can differ in severity and duration from AEs caused by other therapeutic classes. Nivolumab is considered an immuno-oncology agent in this protocol. Early recognition and management of AEs associated with immuno-oncology agents may mitigate severe toxicity.

Management Algorithms have been developed to assist investigators in assessing and managing the following groups of AEs:

- Gastrointestinal
- Renal
- Pulmonary
- Hepatic
- Endocrinopathy
- Skin
- Neurological

The above algorithms are found in the nivolumab Investigator Brochure, and can also be found in [Appendix 6](#) of this protocol.

For subjects expected to require more than 4 weeks of corticosteroids or other immunosuppressants to manage and adverse event, consider recommendations provided in Adverse Event Management Algorithms in Appendix 6.

#### **4.5.2 Dose Delay Criteria**

Tumor assessments for all subjects should continue as per protocol even if dosing is delayed.

##### **4.5.2.1 Nivolumab Dose Delay Criteria**

Nivolumab administration should be delayed for the following:

- Any Grade  $\geq 2$  non-skin, drug-related adverse event, with the following exceptions:
  - Grade 2 drug-related fatigue or laboratory abnormalities do not require a treatment delay
- Any Grade 3 skin, drug-related adverse event
- Any Grade 3 drug-related laboratory abnormality, with the following exceptions for lymphopenia, leukopenia, AST, ALT, or total bilirubin:
  - Grade 3 lymphopenia or leukopenia does not require dose delay
  - If a subject has a baseline AST, ALT or total bilirubin that is within normal limits, delay dosing for drug-related Grade  $\geq 2$  toxicity
  - If a subject has baseline AST, ALT, or total bilirubin within the Grade 1 toxicity range, delay dosing for drug-related Grade  $\geq 3$  toxicity
- Any adverse event, laboratory abnormality, or intercurrent illness which, in the judgment of the investigator, warrants delaying the dose of study medication.

### **4.5.3 Dose Escalations and Reductions**

There will be no dose modification of nivolumab.

#### **4.5.3.1 Criteria to Resume Treatment with Nivolumab**

Subjects may resume treatment with nivolumab when the drug-related AE(s) resolve(s) to Grade  $\leq$  1 or baseline, with the following exceptions:

- Subjects with baseline AST/ALT or total bilirubin in the Grade 1 toxicity range who require dose delays for reasons other than a 2-grade shift in AST/ALT or total bilirubin may resume treatment in the presence of Grade 2 AST/ALT OR total bilirubin
- Subjects with combined Grade 2 AST/ALT AND total bilirubin values meeting discontinuation parameters should have treatment permanently discontinued
- Drug-related pulmonary toxicity, diarrhea, or colitis must have resolved to baseline before treatment is resumed. Drug-related endocrinopathies adequately controlled with only physiologic hormone replacement may resume treatment
- If treatment is delayed  $>$  6 weeks, the subject must be permanently discontinued from study therapy, except as specified in Treatment Discontinuation criteria

#### **4.5.4 Treatment Beyond Disease Progression**

As described in [Section 1.3.3](#), accumulating evidence indicates a minority of subjects treated with immunotherapy may derive clinical benefit despite initial evidence of PD. Subjects treated with nivolumab will be permitted to continue treatment beyond initial RECIST 1.1 defined progressive disease (PD) as long as the following criteria are met:

- 1) Investigator-assessed clinical benefit
- 2) Tolerance of study drug
- 3) Stable performance status
- 4) Treatment beyond progression will not delay an imminent intervention to prevent serious complications of disease progression (eg, CNS metastases)
- 5) Subject provides written informed consent prior to receiving additional nivolumab treatment, using an ICF describing any reasonably foreseeable risks or discomforts, or other alternative treatment options.

The decision to continue treatment beyond initial progression should be discussed with the BMS medical Monitor and documented in the study records.

A radiographic assessment/ scan should be performed within 8 weeks of original PD to determine whether there has been a decrease in the tumor size, or continued PD. The assessment of clinical benefit should be balanced by clinical judgment as to whether the subject is clinically deteriorating and unlikely to receive any benefit from continued treatment with nivolumab.

If the investigator feels that the nivolumab subject continues to achieve clinical benefit by continuing treatment, the subject should remain on the trial and continue to receive monitoring according to the Time and Events Schedule on [Table 5.1-2](#).

For the subjects who continue nivolumab study therapy beyond progression, further progression is defined as an additional 20% increase in tumor burden volume from time of initial PD. This includes an increase in the sum of all target lesions and/ or the development of new measurable lesions. Treatment should be discontinued permanently upon documentation of further disease progression

New lesions are considered measureable at the time of initial progression if the longest diameter is at least 10 mm (except for pathological lymph nodes which must have a short axis of at least 15 mm). Any new lesion considered non-measurable at the time of initial progression may become measureable and therefore included in the tumor burden volume if the longest diameter increases to at least 10 mm (except for pathological lymph nodes which must have a short axis of at least 15 mm).

Subjects with global deterioration of health status (as determined by the investigator) who require discontinuation of treatment without objective evidence of disease progression at the time of treatment discontinuation should be reported as 'symptomatic deterioration'. Every effort should be made to document objective progression (ie, radiographic confirmation) even after discontinuation of treatment.

#### **4.5.4.1 Treatment Discontinuation Criteria for Nivolumab**

Tumor assessments for all subjects should continue as per protocol even if dosing is discontinued.

- **Nivolumab treatment should be permanently discontinued for the following:**
  - Any Grade 2 drug-related uveitis, eye pain or blurred vision that does not respond to topical therapy and does not improve to Grade 1 severity within the retreatment period OR requires systemic treatment
  - Any Grade 3 non-skin, drug-related adverse event lasting > 7 days, with the following exceptions:
    - Grade 3 drug-related uveitis, pneumonitis, bronchospasm, hypersensitivity reaction, or infusion reaction of any duration requires discontinuation
    - Grade 3 drug-related laboratory abnormalities do not require treatment discontinuation except
      - Grade 3 drug-related thrombocytopenia > 7 days or associated with bleeding requires discontinuation
      - Any drug-related liver function test (LFT) abnormality that meets the following criteria requires discontinuation:
        - AST or ALT > 5-10x ULN for > 2 weeks
        - AST or ALT > 10x ULN
        - Total bilirubin > 5x ULN
        - Concurrent AST or ALT > 3x ULN and total bilirubin > 2x ULN
  - Any Grade 4 drug-related adverse event or laboratory abnormality, except for the following events:

- Grade 4 neutropenia  $\leq$  7 days does not require discontinuation
  - Grade 4 lymphopenia or leukopenia does not require discontinuation
  - Isolated Grade 4 electrolyte imbalances/abnormalities that are not associated with clinical sequelae and are corrected with supplementation/appropriate management within 72 hours of their onset do not require discontinuation
  - Isolated Grade 4 amylase or lipase abnormalities those are not associated with symptoms or clinical manifestations of pancreatitis. The Sponsor Medical Monitor designee should be consulted for Grade 4 amylase or lipase abnormalities.
- Any dosing interruption lasting  $>$  6 weeks with the following exceptions:
- Dosing interruptions to manage drug-related adverse events, such as prolonged steroid tapers, are allowed. Prior to re-initiating treatment in a subject with a dosing interruption lasting  $>$  6 weeks, the Sponsor Medical Monitor designee must be consulted. Tumor assessments should continue as per protocol even if dosing is interrupted.
  - Dosing interruptions  $>$  6 weeks that occur for non-drug-related reasons may be allowed if approved by the Sponsor Medical Monitor designee. Prior to re-initiating treatment in a subject with a dosing interruption lasting  $>$  6 weeks, the Sponsor Medical Monitor designee must be consulted. Tumor assessments should continue as per protocol even if dosing is interrupted.

Any adverse event, laboratory abnormality, or intercurrent illness which, in the judgment of the Investigator, presents a substantial clinical risk to the subject with continued nivolumab dosing.

#### **4.5.5 Treatment of Nivolumab-Related Infusion Reactions**

Since nivolumab contains only human immunoglobulin protein sequences, it is unlikely to be immunogenic and induce infusion or hypersensitivity reactions. However, if such a reaction were to occur, it might manifest with fever, chills, rigors, headache, rash, pruritus, arthralgias, hypotension, hypertension, bronchospasm, or other allergic-like reactions. All Grade 3 or 4 infusion reactions should be reported within 24 hours to the study medical monitor and reported as an SAE if it meets the criteria. Infusion reactions should be graded according to NCI CTCAE (Version 4.0) guidelines.

Treatment recommendations are provided below and may be modified based on local treatment standards and guidelines, as appropriate:

**For Grade 1 symptoms: (Mild reaction; infusion interruption not indicated; intervention not indicated).**

- Remain at bedside and monitor subject until recovery from symptoms. The following prophylactic premedications are recommended for future infusions: diphenhydramine 50 mg (or equivalent) and/or acetaminophen/paracetamol 325 to 1000 mg at least 30 minutes before additional nivolumab administrations.

**For Grade 2 symptoms: (Moderate reaction requires therapy or infusion interruption but responds promptly to symptomatic treatment [eg, antihistamines, non-steroidal anti-**

**inflammatory drugs, narcotics, corticosteroids, bronchodilators, IV fluids]; prophylactic medications indicated for ≤ 24 hours).**

- Stop the nivolumab infusion, begin an IV infusion of normal saline, and treat the subject with diphenhydramine 50 mg IV (or equivalent) and/or acetaminophen/paracetamol 325 to 1000 mg; remain at bedside and monitor subject until resolution of symptoms. Corticosteroid and/or bronchodilator therapy may also be administered as appropriate. If the infusion is interrupted, then restart the infusion at 50% of the original infusion rate when symptoms resolve; if no further complications ensue after 30 minutes, the rate may be increased to 100% of the original infusion rate. Monitor subject closely. If symptoms recur, then no further nivolumab will be administered at that visit.
- For future infusions, the following prophylactic premedications are recommended: diphenhydramine 50 mg (or equivalent) and/or acetaminophen/paracetamol 325 to 1000 mg should be administered at least 30 minutes before nivolumab infusions. If necessary, corticosteroids (up to 25 mg of SoluCortef or equivalent) may be used.

**For Grade 3 or 4 symptoms: (Severe reaction, Grade 3: prolonged [ie, not rapidly responsive to symptomatic medication and/or brief interruption of infusion]; recurrence of symptoms following initial improvement; hospitalization indicated for other clinical sequelae [eg, renal impairment, pulmonary infiltrates]. Grade 4: Life-threatening; pressor or ventilatory support indicated).**

- Immediately discontinue infusion of nivolumab. Begin an IV infusion of normal saline and treat the subject as follows: Recommend bronchodilators, epinephrine 0.2 to 1 mg of a 1:1000 solution for subcutaneous administration or 0.1 to 0.25 mg of a 1:10,000 solution injected slowly for IV administration, and/or diphenhydramine 50 mg IV with methylprednisolone 100 mg IV (or equivalent), as needed. Subject should be monitored until the Investigator is comfortable that the symptoms will not recur. Nivolumab will be permanently discontinued. Investigators should follow their institutional guidelines for the treatment of anaphylaxis. Remain at bedside and monitor subject until recovery of the symptoms.

In case of late-occurring hypersensitivity symptoms (eg, appearance of a localized or generalized pruritus within 1 week after treatment), symptomatic treatment may be given (eg, oral antihistamine or corticosteroids).

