### 3.5 Discontinuation of Subjects following any Treatment with Study Drug

Subjects MUST discontinue investigational product (and non-investigational product at the discretion of the investigator) for any of the following reasons:

- Subject's request to stop study treatment
- Any clinical adverse event (AE), laboratory abnormality or intercurrent illness which, in the opinion of the investigator, indicates that continued participation in the study is not in the best interest of the subject
- Termination of the study by Bristol-Myers Squibb (BMS)
- Loss of ability to freely provide consent through imprisonment or involuntarily incarceration for treatment of either a psychiatric or physical (eg, infectious disease) illness
- Study specific criteria for discontinuation of treatment with nivolumab are presented in [Section 4.5.4.1](#).

In the case of pregnancy, the investigator must immediately notify the BMS Medical Monitor/designee of this event. In most cases, the study drug will be permanently discontinued in an appropriate manner. If the investigator determines a possible favorable benefit/risk ratio that warrants continuation of study drug, a discussion between the investigator and the BMS Medical Monitor/designee must occur.

All subjects who discontinue study drug should comply with protocol specified follow-up procedures as outlined in [Section 5](#). The only exception to this requirement is when a subject withdraws consent for all study procedures including post-treatment study follow-up or loses the ability to consent freely (ie, is imprisoned or involuntarily incarcerated for the treatment of either a psychiatric or physical illness).

If study drug is discontinued prior to the subject's completion of the study, the reason for the discontinuation must be documented in the subject's medical records and entered on the appropriate case report form (CRF) page.

**NOTE: A 4-week washout (minimum) of nivolumab is recommended for subjects who are discontinued from treatment with nivolumab for any reason and are being considered for treatment with mTOR inhibitor.**

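### Protocol 4.5.5 gives two dispositions for an infusion reaction that recurs after restart: withhold for that visit (Grade 2 text) or stop permanently (Grade 3 text)

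*Protocol*

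**What the plan says.** Protocol 4.5.5 sets out management by grade.

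- **Grade 2, restart.** The infusion is stopped and symptoms are treated. If it was interrupted, the site is to "restart the infusion at 50% of the original infusion rate when symptoms resolve".
- **Grade 2, recurrence.** "If symptoms recur, then no further nivolumab will be administered at that visit".
- **Grade 2, next bullet.** "For future infusions, the following prophylactic premedications are recommended". This bullet carries no condition about recurrence.
- **Grade 3, definition.** The list of qualifying features includes "recurrence of symptoms following initial improvement" as an item of its own.
- **Grade 3 or 4, action.** "Nivolumab will be permanently discontinued". The acute treatment is also stronger: "Recommend bronchodilators, epinephrine 0.2 to 1 mg of a 1:1000 solution for subcutaneous administration", with IV methylprednisolone among the further options.

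The opening paragraph of 4.5.5 requires CTCAE v4.0 grading and a report to the medical monitor within 24 hours for Grade 3 or 4 reactions. It also allows the treatment recommendations to be adapted to local standards.

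Protocol 4.5.4.1 has a separate stop rule: "Grade 3 drug-related uveitis, pneumonitis, bronchospasm, hypersensitivity reaction, or infusion reaction of any duration requires discontinuation". Protocol 3.5 makes the 4.5.4.1 criteria mandatory. It opens with "Subjects MUST discontinue investigational product (and non-investigational product at the discretion of the investigator) for any of the following reasons" and lists those criteria among the reasons.

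**The concern.** Recurrence on restart is the situation the Grade 2 instruction sets out to cover. It covers it with an action limited to one visit, while the Grade 3 text treats the same event as a reason never to give the drug again. Nothing in the Grade 2 text tells the site to re-grade the event or move to the Grade 3 instructions.

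Sites can therefore diverge. One re-grades, reports within 24 hours and stops nivolumab. Another records Grade 2, ends the visit, and gives the next dose with premedication to a subject who meets a mandatory stop criterion. At stake are that subject's safety, the recorded AE grade, the expedited report and the count of AEs leading to discontinuation. This matters in a single-arm study whose stated purpose is safety and which has no data monitoring committee (Protocol 7).

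**Working it through.** There is no figure in the plan to reproduce. The check sets the instructions side by side and follows one subject through them.

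**Step 1: is a recurrence after restart always a recurrence after improvement?** Yes. The Grade 2 text allows restart only once symptoms have resolved, so any later return of symptoms follows improvement.

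**Step 2: does that event meet the Grade 3 definition as printed?** Yes. The recurrence item is separated from the others by semicolons and does not require prolonged symptoms or hospitalization as well.

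**Step 3: compare the consequences.**

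| | Stays in Grade 2 text | Re-graded to Grade 3 |
|---|---|---|
| Nivolumab that day | None further | None further |
| Later nivolumab | Not ruled out; premedication advised for later infusions | None (4.5.5, 4.5.4.1, 3.5) |
| 24-hour report to medical monitor | Not triggered by grade | Required |
| Recorded grade | 2 | 3 |

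The two routes agree only on the day of the infusion.

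**Step 4: would another rule stop the next dose?** Protocol 4.5.2.1 delays dosing for drug-related non-skin events of Grade 2 or higher. Protocol 4.5.3.1 lets dosing resume at Grade 1 or below, or baseline, and has no exception for infusion reactions. An event left at Grade 2 that has resolved meets no fixed bar. The investigator's general discretion to stop (4.5.4.1) remains.

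**Step 5: timing.** Table 5.1-2 gives dosing every 14 days, plus or minus 2 days, and never less than 12 days apart. The next scheduled dose falls between 14 - 2 = 12 and 14 + 2 = 16 days later.

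**Step 6: would the analysis flag it?** SAP 7.2.2 lists one programmable on-study deviation, continuing therapy after further progression. It has none for failing to stop after a Grade 3 infusion reaction.

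**Step 7: effect on summaries.** With 150 treated subjects, each subject handled one way rather than the other moves the percentage with an AE leading to discontinuation by 1/150 = 0.67 percentage points. SAP 7.6.5 defers that summary to the Core Safety SAP, which is not among the documents, so its exact definition could not be checked. Infusion reactions are not in Protocol Table 6.2.2-1, so the primary IMAE endpoint does not change.

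**The case against.** The best reply is that the instructions can all be obeyed together. Withholding for the visit is a bedside instruction, and permanent discontinuation also means no more drug that day. The sentence does not expressly allow retreatment. A site that grades by CTCAE, as 4.5.5 requires, reaches Grade 3 and then the mandatory rule in 4.5.4.1. On this view only a cross-reference is missing. One can add that the Grade 3 list stands under a description of severe reactions, so a mild symptom on half-rate rechallenge may be just what the Grade 2 bullet was meant for.

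Re-grading and stopping is indeed the correct outcome under the mandatory rule. But the Grade 2 text names recurrence, gives its own action, limits it to one visit and moves on to later infusions. If every recurrence is Grade 3, the one-visit limit is wrong. If some mild recurrences are meant to stay Grade 2, the Grade 3 definition and 4.5.4.1 do not say so. Either way the text needs correcting. The allowance for local practice covers treatment recommendations; it does not extend to grading, the 24-hour report or the stop rule.

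Several limits stand. The Grade 2 bullet does provide supportive treatment (antihistamine, acetaminophen, corticosteroid or bronchodilator as appropriate), so a subject with recurrence is not left without options, although none is tied specifically to the recurrence. The SAP 7.2.2 list contains no toxicity stop rule at all, so that gap is not peculiar to this issue, and site monitoring (Protocol 9.1.2) might find a wrongly given dose. Protocol 4.5.5 itself expects infusion reactions to be unlikely.

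**Conclusion.** The inconsistency is real and the Grade 2 instruction is wrong as written. For an affected subject the difference is between no further nivolumab and a possible dose 12 to 16 days later, together with a different grade and reporting duty. This rests on reading the Grade 3 list literally, on the reaction being drug-related, and, for re-dosing on schedule, on its having resolved.

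The documents give no rate of infusion reactions or of recurrence, so the number of subjects cannot be derived; it is probably small. Sample size, power and the primary endpoint are untouched. The case for acting is subject safety and uniform conduct. The correction should be made, though it does not threaten the study's main result.

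**What to change.** In Protocol 4.5.5, replace the Grade 2 recurrence sentence with:

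> If symptoms recur after restart, stop the infusion, re-grade the event per CTCAE v4.0 (recurrence after initial improvement is Grade 3) and follow the Grade 3 or 4 instructions, including permanent discontinuation and the 24-hour report.

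Limit the bullet on later infusions to Grade 2 reactions without recurrence. If the sponsor does intend retreatment after some recurrences, it should define which ones and write the exception into both 4.5.4.1 and the Grade 3 action in 4.5.5.

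The edit is one sentence and one qualifier, with no new procedures or data. It does need a protocol amendment with ethics committee review (Protocol 9.1.1), and could be carried with the next one. A few subjects with a mild recurrence would lose further drug, which 4.5.4.1 already requires.
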